2. OBJECTIVES

2.1 PRIMARY OBJECTIVE

The primary objective of this study is as follows:

- To investigate the long-term ocular and systemic safety and tolerability of lampalizumab administered ITV monthly

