3.1.1 Patients Enrolled from Study CFD4870g

The extension study enrolled 2 groups of patients from Study CFD4870g: patients previously exposed to lampalizumab and patients who were lampalizumab-naïve (i.e., received sham treatment). Eligible patients who consented to participate in the extension study were enrolled at the conclusion of the Month 18 visit for Study CFD4870g; the Month 18 visit served as the final visit for Study CFD4870g and the Day 1 visit for the extension study. Upon enrollment, all patients received 10-mg ITV injections of lampalizumab. Initially, patients continued on the same dosing frequency (monthly or every-other month) assigned previously during their participation in Study CFD4870g. Patients in the every-other-month treatment arm were later crossed over to the monthly treatment arm for the remainder of their study participation period (see Section 3.3).

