3.3 RATIONALE FOR STUDY DESIGN

The primary objective of the extension study is to assess the long-term ocular and systemic safety and tolerability of lampalizumab in GA patients.

Patients from Study CFD4870g (including those in sham arms), initially received lampalizumab in the extension study at the same dosing frequency previously assigned in Study CFD4870g: patients in the monthly treatment arms continued receiving monthly treatment, and patients in the every-other-month treatment arm *continued receiving every-other-month treatment*.

After Study CFD4870g results demonstrated that monthly administration of lampalizumab had a clinically meaningful and statistically significant effect on reducing the GA area growth over the 18-month study treatment period (see Investigator Brochure for additional details), the every-other-month treatment arm patients were crossed over to the monthly treatment arm for the remainder of their study participation, provided informed consent was obtained.

All patients, regardless of treatment arm in the 6-month GX29455 exposure-response study (including those in sham arms) who are subsequently enrolled in the extension study will be assigned to the 10-mg lampalizumab monthly dosing frequency.

The extension study design will permit an assessment of several exploratory outcomes (see Section 3.4.3) that may offer a better understanding of disease progression and treatment effects.

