4.2 METHOD OF TREATMENT ASSIGNMENT AND MASKING

This is an open-label extension study. All patients enrolled in the extension study will receive 10-mg ITV administrations of lampalizumab.

Dosing frequency in the extension study was either monthly or every other month in accordance with the Study CFD4870g treatment frequency assignment. Patients in the every-other-month treatment arm were later crossed over to the monthly treatment arm for the remainder of their study participation, provided that their informed consents have been obtained. The patients who joined the extension study from Study GX29455 will receive 10-mg ITV administration of lampalizumab monthly.

The patients will remain masked to their previous lampalizumab or sham treatment assignments in Study CFD4870g or Study GX29455 until the Sponsor permits investigators to release this information. The VA examiner will remain masked to patients' study eye assignment and will perform only the VA (including refraction). The VA examiner is not allowed to perform any other tasks involving direct patient care.

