4.3.1.2 Dosage, Administration, and Storage

Dosage

Patients enrolled from Study CFD4870g:

The dose of 10 mg lampalizumab was administered monthly or every other month starting at the Day 1 visit for up to the 18-month of treatment period. Later, the treatment period duration was extended by 24 months and patients in the every-other-month treatment arm were crossed over to the monthly treatment arm to receive monthly study drug treatment for the remainder of their study treatment period, provided that their informed consent has been obtained. The study treatment period *was again* extended by another 24 months *and now by 30 additional months* for a total treatment period of 96 months. Patients in the monthly treatment arm may receive up to 96 ITV injections of study drug. The number of ITV injections of study drug for patients who were in the every-other-month treatment arm prior to their crossover to the monthly treatment arm will vary and will depend on the date of their crossover relative to their Day 1 visit date.

Patients enrolled from Study GX29455:

The extension study will enroll 2 groups of patients from Study GX29455: patients previously exposed to lampalizumab and patients who are lampalizumab-naïve (sham arm). Eligible patients who consent to participate in the extension study will be enrolled at the conclusion of the Week 24 visit for Study GX29455; the Week 24 visit will serve as the final visit for Study GX29455 and the Day 1 visit for the extension study.

All study GX29455 patients enrolled in the extension study will receive 10-mg ITV injections of lampalizumab. Dosing frequency for both treatment arms (Q2W and Q4W) of Study GX29455 changed to monthly dosing *upon entry to this study. Given that 30 months have been added to the original 24 month study duration for the patients from Study GX29455, these patients may receive up to 54 ITV injections of study drug.*

All patients in Study GX29198 will have scheduled monthly visits and monthly study drug treatment for the duration of the study (see [Table 1](#)). The monthly visit will occur relative to the Day 1 visit date. Dosing should not occur earlier than 23 days after the previous dosing. Missed study drug treatments will not be made up *unless an extenuating circumstance applies* (see [Section 3.1.3](#)).

Administration

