4.12 STATISTICAL METHODS

4.12.1 Safety Analysis

Safety will be assessed by adverse events, clinical laboratory evaluations, and immunogenicity as measured by ATA. Safety analyses will include all patients who enrolled into the extension study and received at least one lampalizumab injection *in* the extension study. These patients will be grouped by the treatment received (*lampalizumab or sham*) when they were enrolled in the CFD4870 or GX29455 for safety analyses.

The primary safety analysis is planned to occur at the time when patients enrolled from Study CFD4870g have reached approximately 96 months follow-up and when patients enrolled from Study GX29455 have reached approximately 54 months follow-up.

The timing of the primary analysis may be adjusted according to the start of the open-label extension for Studies GX29176 and GX29185, to which patients from the extension study may have the opportunity to enroll. Earlier safety analyses of this study may be performed on an ad hoc basis.

All verbatim adverse event terms will be mapped to Medical Dictionary for Regulatory Activities (MedDRA) thesaurus terms, and adverse event severity will be graded according to an adverse event severity grading scale (see [Table 3](#)).

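### The Section 4.12.1 grouping pools monthly with early every-other-month extension exposure, so the monthly regimen named in the primary objective is not summarized separately

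*Combined protocol and SAP*

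**What the plan says.** - **Objective.** Section 2.1 names the regimen: "To investigate the long-term ocular and systemic safety and tolerability of lampalizumab administered ITV monthly". Section 3.3 restates the objective without a frequency: "The primary objective of the extension study is to assess the long-term ocular and systemic safety and tolerability of lampalizumab in GA patients".
- **Exposure in the extension.** Section 3.3: "Patients from Study CFD4870g (including those in sham arms), initially received lampalizumab in the extension study at the same dosing frequency previously assigned". Section 4.2 agrees: "Dosing frequency in the extension study was either monthly or every other month in accordance with the Study CFD4870g treatment frequency assignment". Section 3.1.1 adds: "Patients in the every-other-month treatment arm were later crossed over to the monthly treatment arm for the remainder of their study participation period".
- **Crossover.** Section 4.3.1.2 gives no month for it. The number of injections "will depend on the date of their crossover relative to their Day 1 visit date", and the change applied "provided that their informed consent has been obtained". Patients from GX29455 are monthly from Day 1 (Section 3.1.2).
- **Analysis.** Section 4.12.1 takes everyone with at least one extension injection. "These patients will be grouped by the treatment received" in the parent study, with two levels, lampalizumab or sham. The synopsis says the same. Section 4.12.3 adds parent study as a grouping factor, but only for lesion area and visual acuity, and it does not add dosing frequency.
- **Outcome.** Section 3.4.1 makes adverse events the only primary outcome and speaks of incidence. No denominator is given.

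**The concern.** The objective concerns one regimen and the planned tables describe a mixture. Section 3.3 says that former sham patients also started at their assigned frequency, so every-other-month time sits in both reported groups. A reader of the planned output could not tell which events arose on monthly dosing or over how much monthly exposure.

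Section 3.5 ties the ocular risks partly to the route of administration, so a link between risk and number of injections is plausible, though the documents do not show one. If it exists, pooling lowers both the patient-time rate and the proportion of patients with an event relative to monthly dosing. For a safety study that is the unfavourable direction.

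**Working it through.** **The plan's own exposure figures are consistent.** For CFD4870g, 18 + 24 + 24 + 30 = 96 months, and Day 1 plus Months 1-95 gives 96 injections. For GX29455, 24 + 30 = 54 months, and Day 1 plus Months 1-53 gives 54 injections.

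**Assumptions (none is in the documents).**
- p, the share of CFD4870g patients in a group who start every other month: 25-50%.
- X, the crossover month: 6 to 30. Parent Month 18 is extension Day 1, and crossover followed the parent-study results, so late entrants may have crossed early. No minimum is stated.
- d, annual dropout: 0-20%, at a constant hazard h = -ln(1 - d)/12 per month.
- Risk proportional to injections, so the every-other-month rate is half the monthly rate.

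**Formula.** Expected patient-time to month t is PT(t) = (1 - exp(-ht))/h, or t without dropout. The relative understatement of the monthly patient-time rate in CFD4870g is 0.5 × p × PT(X)/PT(96).

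**Results for CFD4870g at month 96.**
- Low end (X = 6, p = 25%, d = 0): 0.5 × 0.25 × 6/96 = 0.8%.
- Middle (X = 18, p = 1/3, d = 0): 0.5 × 0.333 × 18/96 = 3.1%. Such an every-other-month patient has 9 + 78 = 87 injections instead of 96.
- High end (X = 30, p = 50%, d = 20%): PT(30) = 22.99 and PT(96) = 44.75, ratio 0.514; 0.5 × 0.5 × 0.514 = 12.8%. This end needs dropout that leaves 0.8^8 = 17% of patients at month 96.

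**Pooled with GX29455** (assumed share g = 20-40% of patients, 54 months, all monthly). The formula is 0.5 × (1 - g) × p × PT(X) / [(1 - g) × PT(96) + g × PT(54)].
- Low: 0.5 × 0.6 × 0.25 × 6 / (0.6 × 96 + 0.4 × 54) = 0.45/79.2 = 0.6%.
- High: 0.5 × 0.8 × 0.5 × 22.99 / (0.8 × 44.75 + 0.2 × 34.08) = 4.60/42.62 = 10.8%.

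**If only half the monthly risk depends on injections**, the factor 0.5 becomes 0.25 and every figure halves. **Per injection**, with proportional risk, there is no understatement.

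**Proportion of patients with an event.** Take a true 30% on monthly dosing over 96 months, X = 18, p = 1/3, no dropout. Cumulative monthly hazard is -ln(0.7) = 0.357. For every-other-month starters it is 0.357 × 87/96 = 0.323, a proportion of 27.6%. Pooled: (2/3) × 30% + (1/3) × 27.6% = 29.2%. With p up to 50% and dropout up to 20% the pooled figure falls to 27.7%.

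**Earlier cut.** Section 4.12.1 allows the primary analysis date to move and allows ad hoc analyses.
- Cut at month 42, X = 18: from 0.5 × 0.25 × 18/42 = 5.4% to, at 20% dropout, 0.5 × 0.5 × 15.30/29.15 = 13.1%.
- Cut at month 18, crossover at or after it: 0.5 × p = 12.5-25%.

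**The case against.** The study has no control group (Section 3.7), no formal sample size (Section 4.12.5), no hypothesis and no threshold, so nothing turns on a shift of a few percent. Most exposure is monthly in any case, and the pooled table does answer the objective as Section 3.3 words it. Sampling noise may be larger: for an illustrative 100 events, an exact 95% Poisson interval runs from about -19% to +22%. A finer split may also sit in a Data Analysis Plan. All of this stands and limits the weight of the point. It does not close the gap with Section 2.1. "Data Analysis Plan" is only an entry in the abbreviation list, and no such plan is among the documents.

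A reader might infer that the monthly regimen cannot be isolated at all. The documents do not support that. Study drug treatment data enter the extension database (Appendix 1-A, footnote a), adverse events are recorded throughout (Section 3.5), and dose holds have their own eCRF (Section 4.3.1.2). The planned grouping does not separate the regimen, but the data would.

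A reader might also conclude that patients on monthly dosing from Day 1 should become the main description. That is debatable. Pooled across parent studies, that column would include GX29455 patients who had dosing every 2 weeks in the parent study and have at most 54 months of follow-up. It would also set aside post-crossover time that is genuinely monthly.

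**Conclusion.** The point holds in a limited form. Followed as written, Section 4.12.1 and the synopsis produce no summary of the regimen named in Section 2.1, because early every-other-month exposure from CFD4870g is pooled into both groups. If risk rises with injection frequency, the monthly risk is modestly understated: roughly 1-13% in CFD4870g at month 96 with risk proportional to injections, and about 0.6-11% pooled with GX29455.

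These ranges illustrate and do not bound the effect. Arm shares, crossover dates, dropout and the dependence of risk on injections are all assumed, and an earlier data cut would enlarge the figure. It would go too far to say that the safety conclusions are invalid: the documents set no criterion that a shift of this size would change. This is a cheap improvement of modest weight.

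**What to change.** Keep the planned summary and add to Section 4.12.1, and to the synopsis:

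> Within each planned group, and by parent study, adverse events will also be summarized by the extension dosing frequency actually received at onset (monthly; every other month), with patient-time and number of injections for each, split at each patient's recorded crossover to the monthly schedule. Monthly time from Day 1 and monthly time after crossover will be distinguishable. Comparisons are descriptive.

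No column should be named as the main description. If a Data Analysis Plan exists and already contains such a split, a reference to it in Section 4.12.1 would be enough.

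**Cost.** Analysis wording, extra tables and one derived crossover date per patient. If that date is not stored, it has to be derived from dosing records; the Dose Holding eCRF separates holds from scheduled gaps, but missed visits need checking. Cells will be sparse for rare events, and post-crossover time is subject to survivor selection, which a footnote should say. Patient care and data collection do not change.

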4.12.2 Pharmacokinetic and Pharmacodynamic Analyses

Scheduled pharmacokinetic and pharmacodynamic assessments are not planned in the extension study. However, to assist in safety evaluations, serum lampalizumab concentration measurements *may* be performed.

4.12.3 Exploratory Analyses

Mean GA lesion area growth and mean BCVA change from baseline over time will be summarized by treatment group. These patients will be grouped by *parent study and the treatment received (lampalizumab or sham)* when they were enrolled in Study CFD4870g or Study GX29455.

4.12.4 Handling of Missing Data

All efforts will be made to minimize missing data; no imputation will be performed for the safety analysis.

4.12.5 Determination of Sample Size

This study is open to all patients who complete Study CFD4870g or Study GX29455 and who meet eligibility criteria. Accordingly, the sample size for this study is not based on a formal sample size calculation.

4.12.6 Interim Analysis

The primary analysis time will occur as specified in Section [4.12.1](#). Earlier analyses may be performed on an ad hoc basis.

4.13 DATA QUALITY ASSURANCE

The data will be collected via Electronic Data Capture (EDC) using eCRFs. The site will be responsible for data entry into the EDC system. In the event of discrepant data, the CRO will request data clarification from the sites, which the sites will resolve electronically in the EDC system. The CRO will be responsible for the data management of this trial, including quality checking of the data.

Genentech will perform oversight of the data management of this trial. Genentech will produce an EDC Study Specification document that describes the quality checking to be performed on the data. Central Laboratory data and Central Reading Center data will be sent directly to Genentech, using Genentech's standard procedures to handle and process the electronic transfer of these data. eCRFs and correction documentation will be maintained in the EDC system's audit trail. System backups for data stored at Genentech and records retention for the study data will be consistent with Genentech's standard procedures.

5. ASSESSMENT OF SAFETY

5.1 SAFETY PARAMETERS AND DEFINITIONS

Safety assessments will consist of monitoring and recording adverse events, including serious adverse events and adverse events of special interest, performing protocol-specified safety laboratory assessments, measuring protocol-specified vital signs, and conducting other protocol-specified tests that are deemed critical to the safety evaluation of the study.

Certain types of adverse events require immediate reporting to the Sponsor, as outlined in Section [5.2](#).

5.1.1 Adverse Events

According to the ICH guideline for Good Clinical Practice, an adverse event is any untoward medical occurrence in a clinical investigation subject administered a pharmaceutical product, regardless of causal attribution. An adverse event can therefore be any of the following:

- Any unfavorable and unintended sign (including an abnormal laboratory finding), symptom, or disease temporally associated with the use of a medicinal product, whether or not considered related to the medicinal product
- Any new disease or exacerbation of an existing disease (a worsening in the character, frequency, or severity of a known condition), except as described in Section 5.3.5.9
- Recurrence of an intermittent medical condition (e.g., headache) not present at baseline
- Any deterioration in a laboratory value or other clinical test (e.g., ECG, X-ray) that is associated with symptoms or leads to a change in study treatment or concomitant treatment or discontinuation from study drug
- Adverse events that are related to a protocol-mandated intervention, including those that occur prior to assignment of study treatment (e.g., screening invasive procedures such as biopsies)

5.1.2 Serious Adverse Events (Immediately Reportable to the Sponsor)

A serious adverse event is any adverse event that meets any of the following criteria:

- Is fatal (i.e., the adverse event actually causes or leads to death)
- Is life-threatening (i.e., the adverse event, in the view of the investigator, places the patient at immediate risk of death)

This does not include any adverse event that had it occurred in a more severe form or was allowed to continue might have caused death.

- Requires or prolongs inpatient hospitalization (see Section 5.3.5.10)
- Results in persistent or significant disability/incapacity (i.e., the adverse event results in substantial disruption of the patient's ability to conduct normal life functions)
- Is a congenital anomaly/birth defect in a neonate/infant born to a mother exposed to study drug
- Is a significant medical event in the investigator's judgment (e.g., may jeopardize the patient or may require medical/surgical intervention to prevent one of the outcomes listed above)

The terms "severe" and "serious" are not synonymous. Severity refers to the intensity of an adverse event (e.g., rated as mild, moderate, or severe; see Section 5.3.3); the event itself may be of relatively minor medical significance (such as severe headache without any further findings).

Severity and seriousness need to be independently assessed for each adverse event recorded on the eCRF.

Serious adverse events are required to be reported by the investigator to the Sponsor immediately (i.e., no more than 24 hours after learning of the event; see Section 5.2.2 for reporting instructions).

5.1.3 Adverse Events of Special Interest (Immediately Reportable to the Sponsor)

Adverse events of special interest are required to be reported by the investigator to the Sponsor immediately (i.e., no more than 24 hours after learning of the event; see Section 5.2.2 for reporting instructions). Adverse events of special interest for this study include the following:

- Cases of potential drug-induced liver injury that include an elevated ALT or AST in combination with either an elevated bilirubin or clinical jaundice, as defined by Hy's law (see Section 5.3.5.6)
- Suspected transmission of an infectious agent by the study drug, as defined below:
Any organism, virus, or infectious particle (e.g., prion protein transmitting transmissible spongiform encephalopathy), pathogenic or non-pathogenic, is considered an infectious agent. A transmission of an infectious agent may be suspected from clinical symptoms or laboratory findings indicating an infection in a patient exposed to a medicinal product. This term only applies when a contamination of the study drug is suspected.
- Adverse events resulting from medication error
Examples of medication errors include, but are not limited to, overdose, incorrect dose, incorrect route, incorrect drug, incorrect administration, or incorrect kit. If the medication error did result in an adverse event, the primary event term should reflect the adverse event that occurred as a result of the medication error and identify it in "other suspected causes of serious adverse event/ adverse event" data field as a medication error.

- Sight-threatening adverse events

An adverse event is considered to be sight threatening and should be reported expeditiously if it meets one or more of the following criteria:

- It causes a decrease of ≥ 30 letters in VA score (compared with the last assessment of VA prior to the most recent assessment) lasting more than 1 hour
- It requires surgical intervention (i.e., conventional surgery, vitreous tap, or biopsy with intravitreal injection of anti-infectives, or laser or retinal cryopexy with gas) to prevent permanent loss of sight
- It is associated with severe intraocular inflammation (i.e., endophthalmitis, 4 + anterior chamber cell/flare or 4 + vitritis; see Section 5.1.3 for definition and [Appendix 2](#) for intraocular inflammation grading scales)
- In the opinion of the investigator, it may require medical intervention to prevent permanent loss of sight

All above listed sight-threatening adverse events should be reported as serious events, listing the underlying cause (if known) of the event as primary event term.

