Detailed instructions for reconstitution of lampalizumab, pre-injection preparation, administration of the study drug injection, and post-injection procedures for the study eye are provided in the pharmacy binder.

Storage

Detailed instruction for lampalizumab storage is provided in the pharmacy binder.

Lampalizumab Dose-Holding and Study Discontinuation Criteria

Study treatment interruption and/or patient discontinuation from the study (if applicable) due to adverse events will be determined using the criteria listed in [Table 2](#). If any of these criteria are met, treatment will be held and will not be resumed earlier than the next scheduled study visit; with select adverse events, patients may be discontinued from the study. The reason for holding treatment should be recorded on the Dose Holding eCRF and, if applicable, on the Adverse Event eCRF.

Table 2 Dose-Holding or Study Discontinuation Criteria

Event	Dose-Holding or Study Discontinuation Criteria
Intraocular inflammation	Hold dose if intraocular inflammation (iritis, iridocyclitis or vitritis) is $\geq 1+$ in the study eye (see definitions of intraocular inflammation in Section 5.1.3 and inflammation grading scales in Appendix 2); study drug treatment may be permitted subsequently as determined by the investigator. Patients with $\geq 3+$ intraocular inflammation will be discontinued from the study treatment.
VA decrease	Hold dose if there is a treatment-related decrease in BCVA of ≥ 30 letters in the study eye compared with the last assessment of VA prior to the most recent treatment; study drug treatment may be permitted subsequently as determined by the investigator.
IOP	Hold dose if IOP in the study eye is ≥ 30 mmHg. Study drug may be permitted when IOP has been controlled either spontaneously or by treatment as determined by the investigator.
Vitreous hemorrhage	Hold dose in the event of a vitreous hemorrhage in the study eye; study drug treatment may be permitted subsequently as determined by the investigator.
Rhegmatogenous retinal break	Hold dose if a retinal break is present in the study eye. Study treatment may be resumed no earlier than 30 days after successful laser retinopexy as determined by the investigator.
Rhegmatogenous retinal detachment or macular hole	Patients with a rhegmatogenous retinal detachment or Stage 3 or Stage 4 macular holes will be discontinued from the study.

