Appendix 1 Schedule of Assessments (cont.)

Appendix 1-F: Unscheduled Safety Visit Assessments for All Study Patients

Assessments ^a	
Vital signs (blood pressure, respiration rate, temperature, pulse)	x
Physical examination	x
Best corrected visual acuity (4-m starting distance) ^b	x
Slit-lamp examination	x
Dilated binocular indirect high-magnification ophthalmoscopy	x
Intraocular pressure ^c	x
Adverse events ^d	x
Concurrent ocular procedures	x
Concomitant medications	x

^a If determined to be necessary by physician, perform listed assessments. All ocular assessments should be performed on both eyes.

^b Perform finger-counting test followed by hand motion and light perception tests, when necessary.

^c The method used for the IOP measurement for a patient must remain consistent throughout the study.

^d Adverse events causality to be evaluated by the qualified ophthalmologist.

Appendix 2

Grading Scale for Assessment of Anterior Chamber Flare or Cells and Vitreous Cells

Grading Scale for Anterior Chamber Flare or Cells

Flare	
0	No protein is visible in the anterior chamber when viewed by an experienced observer using slit-lamp biomicroscopy; a small, bright, focal slit-beam of white light; and high magnification.
Trace	Trace amount of protein is detectable in the anterior chamber: This protein is visible only with careful scrutiny by an experienced observer using slit-lamp biomicroscopy; a small, bright, focal slit-beam of white light; and high magnification.
1+	Slight amount of protein is detectable in the anterior chamber: the presence of protein in the anterior chamber is immediately apparent to an experienced observer using slit-lamp biomicroscopy and high magnification, but such protein is detected only with careful observation with the naked eye and a small, bright, focal slit-beam of white light.
2-3+	Moderate amount of protein is detectable in the anterior chamber. These grades are similar to 1+ but the opacity would be readily visible to the naked eye of an observer using any source of a focused beam of white light. This is a continuum of moderate opacification, with 2+ being less apparent than 3+.

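### An acuity reading taken between injections can make a loss that reaches Table 2's 30-letter threshold miss the 30-letter criterion for sight-threatening events in Section 5.1.3

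*Combined protocol and SAP*

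**What the plan says.** Two rules in the current protocol text use a 30-letter loss of visual acuity (VA).

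- **Table 2, Section 4.3.1.2 (dose holding):** "Hold dose if there is a treatment-related decrease in BCVA of ≥ 30 letters in the study eye", measured "compared with the last assessment of VA prior to the most recent treatment".
- **Section 5.1.3 (sight-threatening events):** "It causes a decrease of ≥ 30 letters in VA score", measured "compared with the last assessment of VA prior to the most recent assessment) lasting more than 1 hour".

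Section 5.1.3 requires events of special interest to reach the sponsor quickly: "no more than 24 hours after learning of the event; see Section 5.2.2 for reporting instructions". It also sets their classification: "All above listed sight-threatening adverse events should be reported as serious events".

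Acuity is measured before the injection at scheduled visits (Section 4.6.3) and is on the schedule every month (Appendices 1-A to 1-E). It can also be measured when no injection is given. Appendix 1-F lists it for unscheduled safety visits, which Section 4.6.6 provides for when a patient has new ocular symptoms. A dose held under Table 2 is not resumed before the next scheduled visit, where acuity is due again.

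**The concern.** The Table 2 reference stays the same from one injection to the next. The Section 5.1.3 reference, read literally, is the reading immediately before the current one, so it moves with every test. An extra reading between injections therefore resets the starting point for the reporting rule but not for the dose-holding rule. If vision falls in steps, the total loss can reach 30 letters while no single step does.

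At stake are the sight-threatening and serious classification of the event and its 24-hour report. Section 3.5 lists decreased acuity among the potential ocular risks and relies on expeditious reporting of serious events and events of special interest for ongoing safety assessment. The letter criterion is the only numerical acuity trigger among the four sight-threatening criteria.

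**Working it through.** The plan gives no figure to reproduce, so the check applies both rules as written to the same readings.

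**Inputs.** The threshold is 30 letters in both rules (Table 2 and Section 5.1.3). The acuity values are illustrative assumptions; the documents give none.

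**Formulas.**
- Table 2 loss = reading before the last injection − current reading.
- Section 5.1.3 loss = immediately preceding reading − current reading.

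| Readings (inj = injection given after the reading) | Table 2 loss | Section 5.1.3 loss | Letter threshold reached |
|---|---|---|---|
| 70 (inj), 38 | 70 − 38 = 32 | 70 − 38 = 32 | both |
| 70 (inj), 55 unscheduled, 38 | 15, then 70 − 38 = 32 | 70 − 55 = 15, then 55 − 38 = 17 | Table 2 only |
| 70 (inj), 52 at a visit without dosing, 40 | 18, then 70 − 40 = 30 | 70 − 52 = 18, then 52 − 40 = 12 | Table 2 only |
| 70 (inj), 54 (inj), 38 | 16, then 16 | 16, then 16 | neither |
| 60 (inj), 66 unscheduled, 36 | −6, then 60 − 36 = 24 | −6, then 66 − 36 = 30 | Section 5.1.3 only |

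Row 1 shows that the references coincide under regular dosing with no interim reading. If a visit is missed altogether, no reading is taken and the references still coincide. Rows 2 and 3 are the gap. Row 5 shows that the rules can also part in the other direction.

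**Upper bound.** The largest step that misses the criterion is 29 letters. One interim reading gives two steps, so up to 2 × 29 = 58 letters can be lost. Two interim readings give 3 × 29 = 87.

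**How a loss can split.** With one interim reading and no gain, a total loss of L letters (L from 30 to 58) has L + 1 whole-letter splits, and 59 − L of them keep both steps below 30. That is 29 of 31 for L = 30, 14 of 46 for L = 45 and 1 of 59 for L = 58; for L = 59 there are none. These counts describe the rule and are not probabilities.

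**Another reading of the phrase.** If *most recent assessment* means the test before today's, the reference lies two tests back. Row 2 would then be captured (70 − 38 = 32). The reference still moves, however: 70 (inj), 60, 50, 39 is a loss of 31 from before the injection but only 60 − 39 = 21 from two tests back.

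**The case against.** **The rules serve different purposes.** Table 2 concerns treatment-related loss in the study eye. Section 5.1.3 names no eye, requires more than 1 hour's duration, and its events are reported whatever their relation to treatment (Section 5.2). A pre-injection anchor is not the obvious choice for an unrelated or fellow-eye event, so the difference could be deliberate. It could equally be a slip of *assessment* for *treatment*. The documents support neither account over the other. The differences in scope stand, but they do not explain why an extra test should reset the reference. Because acuity is tested in both eyes at scheduled visits, a pre-treatment reading should exist for either eye.

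**Other routes remain.** This stands and limits the consequence. An event that misses the letter criterion may still qualify under Section 5.1.3 through surgical intervention, severe intraocular inflammation or the investigator's opinion, or through the general seriousness criteria in Section 5.1.2. A reader might infer that investigator opinion is the only route left; that is wrong.

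**The primary outcome.** A reader might infer that the primary outcome is biased downward. The documents do not support this. Section 3.4.1 covers the nature, frequency and severity of adverse events and names no count of sight-threatening events. The event is still recorded as an adverse event (Sections 5.1.1 and 5.3.1), and if it persists and worsens, its greatest intensity is recorded (Section 5.3.5.3).

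**Who is affected.** A reader might infer that these are all patients with a suspected injection complication. Doses are also held for corticosteroid use, cataract surgery and systemic treatment of infection (Table 2). Nor does every unscheduled visit produce an acuity reading, because a footnote to Appendix 1-F leaves the assessments to the physician's judgement.

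**Conclusion.** The inconsistency is real. When acuity is read between the last injection and the current visit, a stepwise loss can reach the Table 2 letter threshold yet miss the Section 5.1.3 letter criterion, by up to 58 letters in total with one interim reading. If no other criterion applies, the event can lose its sight-threatening and serious classification and its 24-hour report, though not its record as an adverse event.

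This rests on reading *most recent assessment* as the current test, and on the event otherwise satisfying each rule (for Table 2, treatment-related and in the study eye; for Section 5.1.3, lasting more than 1 hour). How often such sequences occur cannot be estimated from the documents.

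A reader might also infer that Table 2 supplies a fixed baseline that catches all stepwise loss. It does not: its reference resets at each injection, and row 4 escapes both rules. The mismatch explains only losses with a reading between injections.

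The point merits a change because it concerns a stated safety-reporting threshold and the correction is small.

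**What to change.** Reconcile Table 2 and Section 5.1.3 on the reference reading, and state the reason for any difference that is kept. This point makes no recommendation on the dose-holding rule.

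In the reporting definition of Section 5.1.3 only, count a loss of 30 letters or more against either the last VA before the most recent study treatment or the immediately preceding VA. An interim test then cannot switch the criterion off. In the table above, rows 2 and 3 would meet the letter criterion (larger losses 32 and 30) and row 5 would still meet it (30). Row 4 would not change (16), so the amendment should not be presented as covering stepwise loss under regular dosing.

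The cost is one phrase in Section 5.1.3, communication to sites, and possibly some additional expedited reports, whose number the documents do not allow to be estimated.
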